5.9 Prior and Concomitant Therapies and Medications

5.9.1 Prior and Concomitant COPD Medications

All prior therapies for COPD taken in the 3 months prior to Visit 1 and all concomitant COPD therapies will be recorded in the eCRF, with the medication, dose, route and start and stop date(s)

and time(s) clearly recorded to document all required washout periods and compliance with the Inclusion and Exclusion Criteria.

Tiotropium use at a stable dose once daily will be administered during the Run-in and Treatment Periods, starting on the morning after Visit 1.

Upon providing informed consent, patients will discontinue COPD medications for the time periods described in Table 3 prior to the Screening visit and will remain off these medications for the duration of the study.

Table 3 Restrictions for COPD Medications Prior to Screening

Medication	Time Interval Prior to Screening Visit
Oral COPD therapies – e.g. oral steroids, theophylline, roflumilast (Oral mucolytics allowed)	3 months
Antibiotics	3 months
Terbutaline	1 day
Short-acting antimuscarinics (e.g., ipratropium)	1 day
Once or twice daily bronchodilators (LAMA, LABA or LAMA/LABA)	48 hours
Inhaled corticosteroids	4 weeks
Nebulized therapies (other than study medication)	1 week if a bronchodilator 4 weeks if an ICS

Abbreviations: COPD=chronic obstructive pulmonary disease; ICS=inhaled corticosteroids; LABA: long acting β 2 agonist; LAMA=long acting muscarinic antagonist

The following therapies are subject to restriction as indicated:

- Patients must continue to take their background tiotropium medication at the same dose and regimen throughout the Run-in and Treatment Periods. Starting or stopping tiotropium or changes in dosing is not allowed.
- Albuterol may be used as a rescue medication (see Section 5.10), but must be withheld for at least 6 hours prior to spirometry (per below), and this is to be confirmed in the spirometry system. If this withhold is not met, the patient should be rescheduled for a repeat visit within permitted windows. Short acting bronchodilators should be withheld as follows:
 - 6 hours prior to pre-reversibility spirometry at Visit 1 for Screening
 - 6 hours prior to pre-dose spirometry for all subsequent visits
 - Until the completion of all spirometry assessments for all visits

If following the above requirements provide inadequate symptom control, patients should contact the Investigator.

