6 STUDY PROCEDURES AT EACH VISIT

The study will consist of seven visits:

- Pre-Screening (Visit 0), occurring between 2 and 28 days before Visit 1 (sufficient to allow for washout of prohibited medications)
- Screening (Visit 1), occurring 14 (± 1) days prior to the first study treatment administration. Screening procedures ideally should occur over the course of a single day, but may be done over more than one day if necessary. All Screening procedures must be performed prior to initiation of the run-in (i.e., administration of open-label tiotropium)
- Five treatment visits (Visit 2 to Visit 6) each separated by 7 (± 1) days

The schedule of assessments at each visit is shown in Table 4 and listed in Section 6.1 to Section 6.6. The study assessments are described in Section 7.

Post-dose assessments generally should be performed in the following order (as applicable): 1) 12-lead ECG, 2) vital signs, 3) PK blood sample, 4) spirometry.

Table 4 Schedule of Assessments

Visit	Visit 0 Pre-Screen	Visit 1 Screening (Week -2 ±1 d)	Visit 2 Randomiza- tion	Visit 3 (Week 1 ±1 d)	Visit 4 (Week 2 ±1 d)	Visit 5 (Week 3 ±1 d)	Visit 6 End of Study (Week 4 ±1 d or ET)	Telephone Follow-up (1 week after Visit 6 ±2 d)
Informed consent	X							
Assign patient number	X							
Dispense albuterol^(a)	X							
Prohibited medication washout	X							
Demographics		X						
Medical/surgical & disease history		X						
Inclusion/exclusion criteria		X	X					
Randomization criteria			X					
Prior/concomitant medications/therapies		X	X	X	X	X	X	
Physical examination		X						X
Height and body weight		X						X ^(b)
mMRC questionnaire		X	X					
12-lead ECG (QTcF and heart rate)		X	X ^(c)	X ^(c)				X ^(c)
Vital signs (blood pressure, pulse)		X	X ^(d)	X ^(e)	X ^(e)	X ^(e)		X ^(d)
Laboratory safety tests		X						X
Urinalysis		X						X
Viral serology		X						
Pregnancy test^(f)		X	X					X
Reversibility test		X						
Chest X-ray (if needed)		X						
Adverse event questioning		X	X	X	X	X	X	X
Slow spirometry (inspiratory capacity) - 30 min & +2 hours^(g)			X					X
Forced spirometry -30 min to +12 hours^(h)			X					X
Forced spirometry -30 min to +3 hours⁽ⁱ⁾				X	X	X		

Visit	Visit 0 Pre-Screen	Visit 1 Screening (Week -2 ±1 d)	Visit 2 Randomiza- tion	Visit 3 (Week 1 ±1 d)	Visit 4 (Week 2 ±1 d)	Visit 5 (Week 3 ±1 d)	Visit 6 End of Study (Week 4 ±1 d or ET)	Telephone Follow-up (1 week after Visit 6 ±2 d)
Dispense tiotropium		X	X					
Dispense symptom e-diary		X						

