6.3 Visit 1 (Screening)

Patients will be screened to determine eligibility against the Inclusion and Exclusion Criteria 14 days before the first dose of study treatment. Patients must observe the medication restrictions described in Section 5.9.1, and other restrictions described in Section 6.1. To account for diurnal variability in pulmonary function, the Screening visit is to take place in the morning.

The following assessments will be performed, generally in the order indicated (to the extent feasible):

- Demographic information, height and body weight
- Medical/surgical and disease history, including assessment of chronic bronchitis (see Section 7.1.2)
- Prior medications and therapies
- mMRC questionnaire
- 12-lead ECG
- Vital signs
- Physical examination
- Pre-albuterol spirometry
- Reversibility test (four puffs of albuterol)
- Post-albuterol spirometry (20 to 30 minutes after administration)
- Urinalysis

- Blood samples for laboratory safety tests (hematology and blood chemistry), viral serology and serum pregnancy (the latter for women of childbearing potential)
- Urine pregnancy test (for women of childbearing potential). The result should be obtained prior to chest X-ray for females of childbearing potential
- Chest X-ray (unless historical X-ray performed in last 12 months is available)
- Questioning for adverse events

If the patient meets all of the Inclusion and none of the Exclusion Criteria:

- Dispensing of tiotropium and instructions on its use
- Dispensing of e-diary and instructions on its use. The patient will log into the electronic device and answer all of the questions to ensure comprehension (see Section 7.2.2)

The patient will be instructed on the following:

- Instruct patient to return in 14 days for Visit 2
- Observe the medication restrictions described in Section 5.9.1, and other restrictions described in Section 6.1
- Contact the site for any significant increase in COPD symptoms

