- Withhold use of all long acting (once or twice daily) bronchodilators (except for tiotropium)
- Return in 7 days (± 1 day) for the next visit
- Observe the medication restrictions described in Section 5.9.1, and other restrictions described in Section 6.1
- Contact the site for any significant increase in COPD symptoms

6.6 *Treatment Period: Visit 6 (End of Study [or Early Termination])*

Patients will return for the final visit 4 weeks post-randomization. The visit shall be scheduled to begin in the morning, such that dosing occurs within 1 hour of the time of administration at Visit 2.

Patients must withhold all medications described in Section 5.9 prior to treatment in accordance with the washout times provided. If not, the visit must be rescheduled so as to occur within the permitted windows. All restrictions defined in Section 6.1 should also be adhered to.

6.6.1 *Pre-dose Assessments*

The following assessments will be performed prior to dosing:

- Concomitant medications; confirm that medications were withheld as required

- Unblinded study staff will collect nebulizer, compressor and any used/unused study medication
- Collect e-diary and review for compliance with the device
- Assessment of tiotropium and study medication compliance
- Questioning for adverse events
- Physical examination and body weight
- Blood samples for laboratory safety tests
- Urinalysis
- Urine pregnancy test (females of childbearing potential only)
- 12-lead ECG
- Vital signs
- SGRQ-C, TDI, CAT and PGAC questionnaires
- Slow spirometry (to obtain inspiratory capacity), performed 30 (\pm 10) minutes pre-dose
- Forced spirometry, performed following completion of slow maneuver
- Administration of tiotropium

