9.3.2 Secondary Endpoints

- Change from baseline in average AUC_{0-3h} FEV₁ at Visits 2 to 6
- Change from baseline in average AUC_{0-12h} FEV₁ at Visits 2 and 6
- Change from baseline in peak FEV₁ at Visits 2 to 5
- Change from baseline in morning trough FEV₁ at Visits 3 to 6
- Change from baseline (i.e., mean over the last 7 days of Run-in) to the mean weekly values over weeks 1 to 4 in COPD symptoms, as measured by daily e-diary (E-RSTM:COPD)
- Change from baseline in the SGRQ-C questionnaire at Visits 4 and 6
- TDI questionnaire at Visits 4 and 6
- PGAC questionnaire at Visits 4 and 6
- Change from baseline (i.e., mean over the last 7 days of Run-in) to the mean weekly values over weeks 1 to 4 in rescue medication use
- Change from baseline in peak and average AUC_{0-3h} FVC at Visits 2 to 6, in average AUC_{0-12h} FVC at Visits 2 and 6 and in morning trough FVC at Visits 3 to 6.

- Trough plasma concentration of tiotropium at Visits 2 and 4, and trough plasma concentration of RPL554 at Visit 4
- Safety and tolerability:
 - Continuous monitoring of adverse events
 - Laboratory safety tests (hematology, blood chemistry and urinalysis)
 - 12-lead ECG (including QTcF and heart rate), supine vital signs (blood pressure and pulse rate)

9.3.3 *Exploratory Endpoints*

- Change in peak and average AUC_{0-12h} FEV₁ between Visits 2 and 6
- Change from baseline in IC after 4 weeks of treatment
- Change from baseline in the CAT questionnaire at Visits 4 and 6
- Change from baseline (i.e., mean over the last 7 days of Run-in) to the mean weekly values over weeks 1 to 4 in morning symptoms
- Change from baseline (i.e., mean over the last 7 days of Run-in) to the mean weekly values over weeks 1 to 4 in morning activity limitation

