16.2.1.4. RESCUE MEDICATIONS

Rescue medication use will be presented for the FAS set.

Baseline use of rescue medication is the mean over the last 7 days of run-in phase, using only days where data was recorded:

$$\frac{\text{Sum of number of puffs taken}}{\text{days recorded}}$$

Use of medication per visit is calculated as the mean use daily over total number of days between previous visit (inclusive) and the following visit, e.g. Week 1 is defined as the period between Visit 2 and Visit 3, calculated only based on the days data was recorded/verified. For the last visit, when patient completes the study the derivation will use days between previous visit (inclusive) and the following/last visit (inclusive).

If less than 4 days of data are available for the week, the weekly mean is set to missing, e.g. if data is entered for less than 4 days between Visits 2 and 3 then no result will be presented for Week 1.

If a patient discontinued then use treatment study end date, as the date of their last expected visit. This will be documented in the "Rescue Medication" page of the eCRF, as well as in the "Rescue Medication Use" diary entry.

The rescue medication use will be confirmed in the diary using the following rules:

1. If patient has put in rescue medication use then analyse as expected
2. If patient has not put in rescue medication use, then to confirm that there was no diary compliance issue, or IT issue, question "No Rescue Medication Confirmation" will be checked to make sure it is filled in correctly.
3. If patient has not put in rescue medication use and question "No Rescue Medication Confirmation" was not filled in correctly then this will be treated as diary compliance or IT issue and therefore this day will not be used as the day recorded for the weekly means calculation.

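### Weekly rescue means include clinic days on which albuterol is to be withheld, while the baseline week has none, so on-treatment use is modestly under-counted

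*SAP*

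**What the plan says.** - **On-treatment weeks.** SAP 16.2.1.4 takes the "mean use daily over total number of days between previous visit (inclusive) and the following visit". Week 1 therefore holds the Visit 2 day, Week 2 the Visit 3 day and Week 3 the Visit 4 day. For completers, Week 4 holds both Visit 5 and Visit 6: "For the last visit, when patient completes the study the derivation will use days between previous visit (inclusive) and the following/last visit (inclusive".
- **Baseline.** SAP 16.2.1.4: "Baseline use of rescue medication is the mean over the last 7 days of run-in phase, using only days where data was recorded". This matches the endpoint in Protocol 9.3.2: "Change from baseline (i.e., mean over the last 7 days of Run-in) to the mean weekly values over weeks 1 to 4 in rescue medication".
- **Visit timing.** Protocol 6: "Five treatment visits (Visit 2 to Visit 6) each separated by 7" (±1) days. The last scheduled visit before Visit 2 is Screening. Protocol 6.3: "Patients will be screened to determine eligibility against the Inclusion and Exclusion Criteria 14 days before the first dose of study treatment".
- **Withhold.** Protocol 5.9.1 has short-acting bronchodilators withheld from 6 h before pre-dose spirometry and "Until the completion of all spirometry assessments for all visits". By the footnotes to Protocol Table 4, spirometry runs from 30 min pre-dose to 3 h post-dose at Visits 3 to 5, and to 12 h at Visits 2 and 6.
- **Recording.** Protocol 5.10 still allows albuterol during a visit if the patient needs it. Site staff record it on the eCRF, and use between visits goes in the e-diary. At Visit 6 the pre-dose list in Protocol 6.6.1 includes "Collect e-diary and review for compliance with the device".
- **Analysis.** SAP 16.2.2 analyses change from baseline with the MMRM used for the primary endpoint.

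No SAP text excludes or adjusts for clinic days in this endpoint. The rescue-related sensitivity analysis in SAP 16.5 concerns average FEV₁ AUC over 12 h only. SAP 16.2.1.4 names both the eCRF page and the diary but does not say whether eCRF puffs enter the weekly sum.

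**The concern.** The effect on rescue albuterol use is a stated secondary objective. On a clinic day, the puffs recorded reflect the visit rule as well as the patient's need. Every on-treatment week contains at least one such day and the baseline week contains none. A patient whose need has not changed would appear to improve, by an amount that depends on the week. The difference between RPL554 and placebo in puffs/day would also be scaled down, because fewer hours in each on-treatment week are free for need-driven use. The effect estimate would then understate what happens on ordinary days, and the week-to-week pattern would partly reflect the visit schedule.

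**Working it through.** **Plan's own figure.** The documents give no rate, SD or effect for rescue use, so there is no stated figure to reproduce. The sample size for peak FEV₁ does reproduce: 93 mL, SD 200 mL, 5% two-sided and 80% power give 73 per group. It serves below only as the arm size.

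**Length of the withhold** = 6 h + 0.5 h + time of last post-dose spirometry.
- Visits 3 to 5: 6 + 0.5 + 3 = 9.5 h, which is 9.5/24 = 0.396 of a day.
- Visits 2 and 6: 6 + 0.5 + 12 = 18.5 h, which is 18.5/24 = 0.771 of a day.

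Morning dosing is between 7 and 10 am (Protocol 5.4.2), so the withhold starts between about 00:30 and 03:30. It falls on the visit date itself.

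**Baseline week.** Screening is 14 (±1) days before first dose, so the last 7 run-in days hold no scheduled visit.

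**Share of weekly use lost** = sum of the withheld day-fractions / days in the window. This assumes even use over 24 h, no make-up puffs, no in-clinic rescue and visits 7 days apart.
- Week 1: 0.771/7 = 11.0%.
- Weeks 2 and 3: 0.396/7 = 5.7%.
- Week 4, Visit 6 day unrecorded and dropped: 0.396/7 = 5.7%.
- Week 4, Visit 6 counted with 18.5 h withheld: (0.396 + 0.771)/8 = 14.6%.
- Week 4, Visit 6 counted as a day with zero puffs: (0.396 + 1)/8 = 17.4%.

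**How far the assumptions move this.**
- Visits 6 to 8 days apart: Week 1 9.6% to 12.8%; Weeks 2 and 3 4.9% to 6.6%.
- Use only between 06:00 and 22:00, dosing at 07:00 to 10:00: Week 1 11.6% to 14.3%; Weeks 2 and 3 3.6% to 6.2%; Week 4 with Visit 6 counted as a restricted day 13.3% to 18.0%.
- Half of the forgone puffs taken later and recorded: 5.5%, 2.8% and, in Week 4, 2.8% (Visit 6 dropped) to 7.3% (Visit 6 counted as a restricted day). All taken later and recorded: 0%. In the zero-day case, puffs taken after the diary is handed in cannot enter it.

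**In puffs/day.** For an assumed 2 puffs/day with no true change, the apparent change is −0.22 in Week 1, −0.11 in Weeks 2 and 3, and −0.11 to −0.35 in Week 4 (2 × 0.057 to 2 × 0.174). At 1 and 4 puffs/day these halve and double.

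**Effect on the comparison.** If both arms lose the same share f, the expected difference is (1 − f) × the true difference. With no true difference it stays at zero. An illustrative Week 4 simulation used 2,000 runs, 73 per arm, an assumed 3 puffs/day, an assumed rate ratio of 0.7, a baseline-adjusted model, and Visit 6 as a restricted day:
- SAP rule: placebo change −0.44, treatment difference −0.76, power 93%.
- Non-clinic days only: placebo change about 0.00, treatment difference −0.89, power 92%.
- Type I error was about 5% under both rules.

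**The case against.** The strongest defence is that the withhold is the same in every randomized arm. The MMRM has visit and treatment-by-visit terms, so a fall common to all arms drops out of each contrast with placebo. What remains is a rescaling, and the SD shrinks almost in proportion, so tests are hardly affected. All of this stands. A reader might infer that the rule could make RPL554 look effective when it is not, or that it costs material power. The documents and the simulation support neither.

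The withhold is also less absolute than the hours suggest. Protocol 5.9.1 is mandatory about the 6 h before spirometry but advisory about the time until spirometry ends, and Protocol 5.10 provides for in-clinic rescue. So it would be too strong to say that the restricted hours carry no treatment signal. Whether that signal reaches the endpoint depends on whether eCRF puffs are summed, which the SAP leaves open.

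The 17% figure for Week 4 is equally tempting and equally unproven. It needs a diary entry or a confirmed no-rescue answer about the Visit 6 date, made before the diary is collected. The documents do not give the recall period of the rescue question. If it is asked at bedtime, no Visit 6 entry exists, the day is dropped, and the loss is about 6%. If it is asked in the morning about the day before, the entry describes a home day and the loss is 0.396/8 = 4.9%. It is therefore not established that Week 4 is among the worst-affected weeks.

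Finally, patients may make up forgone puffs in the evening, and the documents give no information on this. None of these points makes the baseline and on-treatment weeks alike.

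**Conclusion.** The point holds as a modest measurement problem on a secondary endpoint. As written, the SAP compares a baseline with no scheduled clinic day against weeks containing one or two restricted days, and nothing else in either document corrects for it. With even use, no make-up puffs and no in-clinic rescue, the under-count is about 11% (Week 1), 6% (Weeks 2 and 3) and 6% to 17% (Week 4). Half make-up that is recorded halves the figures that assume none, and full recorded make-up removes them.

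Two things are affected: the within-arm change, which shows an artificial fall of varying size by week, and the size of the puffs/day difference from placebo, which shrinks by the same shares. The validity of the treatment comparison and its power are not in question. The rescue rate is an assumption throughout. The rule is worth changing because the remedy is cheap and makes the two periods like for like.

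**What to change.** In SAP 16.2.1.4, before unblinding:

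1. Compute each weekly rescue mean from non-clinic days only. Leave the diary records that cover the dates of Visits 2, 3, 4, 5 and 6 out of both numerator and denominator, and keep the 4-day minimum. State the recall period of the diary question, so that it is clear which record covers a visit date.
2. State that in-clinic albuterol from the eCRF does not enter the weekly mean, and summarise it separately by arm and visit.
3. Keep the all-days mean as a sensitivity analysis, with an explicit rule for the Visit 6 day and for eCRF puffs.

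This uses data already collected and changes no clinical procedure. The cost is one fewer day per weekly mean, or two fewer in Week 4. With visits 7 (±1) days apart, 5 to 7 days remain: 6 to 8 less one in Weeks 1 to 3, and 7 to 9 less two in Week 4. The means will be slightly noisier, and a few more weeks may fall below 4 recorded days. The endpoint then describes use on non-clinic days, and need-driven use during visits is reported outside it.

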16.2.2. Analysis of Secondary Efficacy Variables

PD parameters (trough FEV₁, peak FEV₁, FEV₁ AUC_{0-T}, trough FVC, peak FVC and FVC AUC_{0-T}), rescue medication, average weekly E-RSTM:COPD, SGRQ-C, TDI and PGAC scores will be analysed using an MMRM approach, as described in Section 16.1.2 for the primary endpoint. The change from baseline will be analysed for all endpoints except TDI and PGAC. The BDI will be used as baseline for TDI. The baseline term will not be included in the MMRM analysis of PGAC.

For exploratory purposes, the subdomain scores of E-RSTM:COPD and SGRQ-C will also be summarised and analysed in the same way.

A plot of the mean change from baseline FEV₁ to each post-dose FEV₁ result over time will be created by visit and treatment group.

The number of patients experiencing at least one COPD exacerbation and the number of exacerbations will be summarized by treatment group.

Individual questions for E-RS and SGRQ-C questionnaires will be listed.

A plot of the least squares means change from baseline to total score E-RS over time will be presented (based on the MMRM analysis).

Furthermore, an analysis of the proportion of responder patients, with an improvement from baseline in SGRQ-C total score of 4 or more, will be summarised by visit and treatment group and analysed using logistic regression. The model for each visit will include randomised treatment groups and actual reversibility strata as factors. Patients with a missing response, either due to withdrawal or that the SGRQ-C questionnaire was not filled in properly, will be assumed to be a non-responder.

A bar chart of the percentage of responders at each visit will also be presented by treatment group.

Total score will be used for the TDI analysis; BDI and TDI total and subdomain scores will be listed.

The secondary efficacy analyses (excluding the PK summaries) will be performed on the FAS set. The PK results will be summarised for the PKS set.

The analyses of the secondary safety endpoints are described in Section 17.

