7. STATISTICAL CONSIDERATIONS

7.1. Adjustments for Covariates and Factors to be Included in Analyses

The following covariates and factors will be used in the analyses. For details of their inclusion in the models, see the specific analysis section.

- Fixed effects: treatment (RPL554 0.375 mg, RPL554 0.75 mg, RPL554 1.5 mg, RPL554 3 mg, Placebo), visit (Day 1, Weeks 1, 2, 3 and 4), visit*treatment, actual reversibility strata (reversible, non-reversible)
- Random effect – patient
- Covariate – baseline

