16.1.2. Primary Analysis of Primary Efficacy Variables

Peak FEV_1 will be summarised as actual value at Week 4 and change from baseline FEV_1 to peak FEV_1 at Week 4 using descriptive statistics for all treatment groups.

Peak FEV_1 will be computed as the maximum value in the 3 hours after dosing. Baseline FEV_1 is the latest measurement taken before study drug on the day of first dosing, i.e. 30 minutes pre-dose at Day 1.

The primary objective of this study is to test the hypothesis that there is a difference between different dose levels of study treatment (RPL554) in comparison with placebo, all administered by nebulizer and added on to tiotropium. The change from baseline FEV_1 to peak FEV_1 will be compared between the treatments using a mixed model for repeated measures (MMRM) with fixed effects for treatment, visit and treatment by visit interaction, patient as random effect and baseline as covariate. An unstructured covariance structure will be used to model the within-patient errors. If the model does not converge a compound symmetry covariance structure will be used. Kenward-Roger method will be used to estimate the model degrees of freedom.

Treatment comparisons will be summarised using mean effect differences with 95% CI and associated 2-sided p-values.

Firstly, RPL554 treatments will be compared to placebo using a closed testing procedure. The testing will begin with the highest dose (3 mg) compared to placebo. If found statistically significant then the lower dose (1.5 mg) will be compared to placebo. If found significant then the next lower dose will be compared to placebo until either all doses are compared to placebo, or a result is found to be non-significant and therefore the comparison ends. Secondly, the doses will be compared in a pairwise fashion as shown in Table 2, below.

Document: ...\\Verona_Pharma\\RPL554\\BZA48916\\Biostatistics\\Documentation\\SAP\\Verona CO-205 SAP v1.0

Author: [REDACTED] Version Number: V1.0

Version Date: 05DEC2019

Template No.: CS_TP_BS016 Revision 5

Reference: CS_WI_BS005

Effective Date: 01Apr2018

Table 2: Pairwise comparison between the RPL554 treatment groups:

RPL554 dose	[REDACTED]	[REDACTED]	[REDACTED]	[REDACTED]	[REDACTED]	[REDACTED]
	[REDACTED]	[REDACTED]	[REDACTED]	[REDACTED]	[REDACTED]	[REDACTED]
	[REDACTED]	[REDACTED]	[REDACTED]	[REDACTED]	[REDACTED]	[REDACTED]
	[REDACTED]	[REDACTED]	[REDACTED]	[REDACTED]	[REDACTED]	[REDACTED]

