$$Score = 100 * \frac{\text{Sum of weights from all positive items in that questionnaire}}{\text{Sum of maximum weights for all items in that questionnaire}}$$

The higher the score the more severe impact of COPD on patient's life.

16.2.1.2.3.□□□□□ BDI/TDI

BDI and TDI are questionnaires that focus on three subdomains: Functional impairment, Magnitude of task and Magnitude of effort. BDI is collected at baseline (Day 1) and TDI is collected post-baseline (Weeks 2 and 4).

Subdomain score is calculated as the sum from the related questions.

Total score is calculated as the sum of the subdomain scores.

If at least one of the scores is missing, then total score is set to missing.

16.2.1.2.4.□□□□□ PGAC

Patient Global Assessment of Change (PGAC) is a single question assessment to determine whether patients have noticed a change in their breathing since the start of the study.

16.2.1.2.5.□□□□□ CAT

CAT is designed to assess further the COPD symptoms. There are 8 subdomains, each having only one question and these include Cough, Mucus, Chest Tight, Breathless, Limited Activities, Confident, Sleep and Energy. Each question is scored 1-5. The higher the score the more severe impact of COPD on patient's life.

Document: ...\\Verona_Pharma\\RPL554\\BZA48916\\Biostatistics\\Documentation\\SAP\\Verona CO-205 SAP v1.0

Author: [REDACTED] Version Number: V1.0

Version Date: 05DEC2019

Template No.: CS_TP_BS016 Revision 5

Reference: CS_WI_BS005

Effective Date: 01Apr2018

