16.3.2. Analysis of Exploratory Efficacy Variables

Peak FEV₁, CAT scores, morning symptoms and morning activity limitations will be analysed using an MMRM approach, as described in Section 16.1.2.

Due to AUC_{0-12h} FEV₁ only being derived for Day 1 and Week 4, an ANCOVA analysis of the change from baseline will be performed with fixed effects for treatment and actual reversibility strata, and baseline as a covariate. Each measurement will be graded based on the quality of the measurement. Grades "Acceptable" and "Borderline Acceptable" will be used in the analyses, as

Document: ...\\Verona_Pharma\\RPL554\\BZA48916\\Biostatistics\\Documentation\\SAP\\Verona CO-205 SAP v1.0

Author:  Version Number: V1.0

Version Date: 05DEC2019

Template No.: CS_TP_BS016 Revision 5

Reference: CS_WI_BS005

Effective Date: 01Apr2018

these will indicate usable measurements. Grade “Unacceptable” will not be used in the analysis, as the measurement will be identified as poor quality.

Total score data will be used for the CAT questionnaire analysis.

An analysis of the proportion of patients with an improvement from baseline in CAT total score of 4 or more will be summarised by visit and treatment group and analysed using logistic regression. The model will include randomised treatment groups and actual reversibility strata as factors. Patients with a missing response will be assumed to be a non-responder. Also, total score and subdomain scores will be listed. A plot of the least square means change from baseline in total score over time will be presented (based on the MMRM analysis).

Due to IC only being collected on Day 1 and at Week 4 for two timepoints 30 minutes pre-dose and 2 hours post-dose, an ANCOVA analysis of the change from baseline (Day 1, 30 minutes pre-dose) to remaining 3 timepoints will be performed with fixed effects for treatment and actual reversibility strata, and baseline as a covariate. Each measurement will be graded based on the quality of the measurement. Grades “Acceptable” and “Borderline Acceptable” will be used in the analyses, as these will indicate usable measurements. Grade “Unacceptable” will not be used in the analysis, as the measurement will be identified as poor quality.

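### The SGRQ-C and CAT responder models omit the baseline score: valid on average, but they give up some power and leave chance baseline imbalance in the odds ratios

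*SAP*

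**What the plan says.** SAP 16.2.2 applies logistic regression to SGRQ-C response, meaning a total score at least 4 points better than at baseline. The terms are stated in full: "The model for each visit will include randomised treatment groups and actual reversibility strata as factors". A patient with a missing response "will be assumed to be a non-responder".

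SAP 16.3.2 does the same for CAT: "An analysis of the proportion of patients with an improvement from baseline in CAT total score of 4 or more" is modelled by logistic regression, and "The model will include randomised treatment groups and actual reversibility strata as factors". SAP 16.5 repeats the SGRQ-C responder analysis with LOCF in place of the non-responder rule, using the same two factors.

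SAP 7.1 lists baseline among the covariates but adds: "For details of their inclusion in the models, see the specific analysis section". Those sections do not name it for the responder models. The continuous SGRQ-C and CAT scores use the MMRM of SAP 16.1.2, which has "patient as random effect and baseline as covariate".

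**The concern.** The baseline score enters the definition of response, so it predicts response. High scorers tend to fall and low scorers to rise on re-measurement, and a patient close to the bottom of a scale has little room to improve by 4. Reversibility to albuterol is not a substitute for a symptom score.

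The omission also departs from the SAP's own practice. Baseline is a covariate in the MMRMs and in the ANCOVAs, and the BDI serves as baseline for the TDI. Where the SAP drops baseline, for PGAC, it says so. For the responder models it gives no reason, so the same questionnaire is baseline-adjusted as a score and unadjusted as a response.

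At stake is noise in the comparisons of dose with placebo. All four share one placebo arm, so a chance baseline difference in that arm moves all four odds ratios in the same direction. Protocol 1.1 says the study is meant to support dose selection for Phase III.

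**Working it through.** **1. The plan's own figure.** The documents give no power or sample size for the responder analyses. The only calculation is for peak FEV₁ (Protocol 9.5): SD 200 mL, difference 93 mL, two-sided 5%, 80% power.

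n = 2 × (1.960 + 0.842)² × (200/93)² = 2 × 7.85 × 4.625 = 72.6, so 73 per group. This reproduces. The check below uses the 80 per group to be randomised.

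**2. How far the floor limits response.** Means and SDs are assumed.

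- SGRQ-C runs from 0 to 100, so only a baseline below 4 rules out response. With mean 45 and SD 17: Φ((4 − 45)/17) = Φ(−2.41) = 0.8%.
- For CAT, SAP 16.2.1.2.5 has eight questions and says "Each question is scored 1-5", giving totals of 8 to 40. A baseline below 8 + 4 = 12 cannot improve by 4. With SD 7: Φ((12 − 18)/7) = 20% at mean 18, and Φ((12 − 21)/7) = 10% at mean 21.

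The floor is negligible for SGRQ-C, where regression to the mean does the work. For CAT, as the SAP scores it, the floor adds to that.

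**3. Chance imbalance.** The baseline difference between two arms of 80 has SD √(2/80) = 0.158 in baseline SD units. The simulations in step 4 give the change in the unadjusted log odds ratio per 1 SD of imbalance:

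| Endpoint | Change per SD | Typical shift (× 0.158) | After adjustment |
|---|---|---|---|
| SGRQ-C | 0.3 to 0.6 | 0.05 to 0.10 | about 0 |
| CAT | 0.6 to 1.0 | 0.10 to 0.16 | about 0 |

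**4. Power.** Two arms of 80, 3,000 simulated trials per scenario, 10% missing set to non-responder; treatment plus stratum, with and without the baseline score. Assumed: SGRQ-C mean 45, SD 17, effect 4 or 6 points; CAT SD 7, effect 2 or 3 points, placebo improvement 1 point, range 8 to 40. Correlation is between baseline and follow-up.

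| Endpoint | Correlation | Smaller effect | Larger effect |
|---|---|---|---|
| SGRQ-C | 0.7 | 26% to 29% | 53% to 56% |
| SGRQ-C | 0.8 | 38% to 41% | 70% to 73% |
| SGRQ-C | 0.9 | 65% to 66% | 94% to 94% |
| CAT, mean 18 | 0.6 | 25% to 29% | 46% to 54% |
| CAT, mean 18 | 0.7 | 31% to 35% | 61% to 67% |
| CAT, mean 18 | 0.8 | 42% to 46% | 74% to 79% |
| CAT, mean 21 | 0.6 | 28% to 31% | 53% to 59% |
| CAT, mean 21 | 0.7 | 36% to 39% | 65% to 70% |
| CAT, mean 21 | 0.8 | 47% to 49% | 83% to 85% |

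Each rate has a Monte Carlo standard error of at most √(0.25/3000) = 0.9 points. With no treatment effect, both models reject near 5% (3.9% to 5.6% in the CAT runs above).

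**5. Where the gain appears.** In one SGRQ-C scenario the log odds ratio goes from 0.440 (SE 0.324) to 0.486 (SE 0.342). The SE rises, but the ratio goes from 0.440/0.324 = 1.36 to 0.486/0.342 = 1.42. On the risk-difference scale precision does improve: the variance of the standardised difference falls by about 2 to 8% for SGRQ-C and 5 to 16% for CAT.

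**The case against.** The case for leaving the models alone is fair in several respects.

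- **Validity.** A reader might infer that the unadjusted odds ratios are biased. The documents do not support that: allocation is random within reversibility strata, chance imbalance averages to zero, and the confidence interval already reflects it. A typical SGRQ-C shift of 0.05 to 0.10 is small beside an SE of about 0.32. This stands.
- **Precision.** It is also tempting to say that the planned models give a wider interval for the odds ratio. Step 5 shows the opposite for the SE. The loss is in power and in the precision of the risk difference. This stands.
- **Floor.** A reader might suppose that many patients cannot be SGRQ-C responders. About 1% cannot, under the assumed distribution, and mMRC of at least 2 at Screening and at Visit 2 makes very low scores less likely. This stands for SGRQ-C. It does not remove the CAT floor, although the 10 to 20% share rests on assumed means and SD.
- **Coverage elsewhere.** The continuous scores already receive a baseline-adjusted MMRM, and the responder models are supplementary, exploratory or a sensitivity analysis. This limits the importance of the point. It does not explain why the response analysis of the same data should discard the covariate.
- **Side effects.** Adjustment makes the odds ratio conditional on baseline, so it no longer matches the raw responder percentages. A patient with no baseline score, now counted as a non-responder, would drop out of the model. Both objections are correct, and the remedy has to deal with them.

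**Conclusion.** The omission is plain in the text of SAP 16.2.2, 16.3.2 and 16.5, and it rests on no assumption. SAP 7.1 does not fill the gap, because it defers to those sections; nor does it contradict them.

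The consequence is modest: about 0 to 3 power points for SGRQ-C, mainly through regression to the mean, and about 2 to 8 for CAT. A typical chance shift in the log odds ratio is 0.05 to 0.10 for SGRQ-C and 0.10 to 0.16 for CAT. These sizes depend on assumed means, SDs, correlations and effects. The CAT figures also depend on the item scoring as the SAP states it.

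It would go too far to say that the trial's conclusions are at risk. Type I error is near 5% with or without the covariate. One secondary responder endpoint, its sensitivity repeat and one exploratory endpoint are affected. The primary peak FEV₁ analysis and the sample size are not. The change is still worth making, because it costs little and is fully credible only if specified before unblinding.

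**What to change.** Before unblinding, amend SAP 16.2.2, 16.3.2 and 16.5:

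1. In each of the three logistic models, add the baseline total score (SGRQ-C or CAT, as applicable) as a continuous covariate beside randomised treatment and actual reversibility stratum.
2. State how a patient with no baseline score is handled. One option that keeps the analysis set intact is to retain the non-responder status already given by SAP 16.4 and enter the mean baseline pooled over arms in the model. The LOCF repeat needs its own sentence, since last known responder status is undefined without a baseline.
3. Report a baseline-standardised risk difference with 95% confidence interval beside the conditional odds ratio: average the model's predicted probabilities over all patients in the model under each treatment, and take the difference. This can be compared with the responder percentages in both sections and the SGRQ-C bar chart.

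**Cost.** There are no new data, since both questionnaires are completed pre-dose at Visit 2 (Protocol 6.4.1). Protocol 9.3.2 and 9.3.3 do not list the responder endpoints, so these models are defined only in the SAP. The price is an odds ratio that is conditional on baseline, and slightly more programming for the standardised difference.
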